6. SYNOPSIS

Study Title: A Multicenter, Open Label Pilot Study to Explore the Efficacy and Safety of Acthar® in Subjects With Severe Noninfectious Intermediate Uveitis, Posterior Uveitis, or Panuveitis	
Protocol MNK61074105	Type: Phase 4
Condition/Disease:	Severe Noninfectious Intermediate Uveitis, Posterior Uveitis, or Panuveitis (NIPPU)
Approximate Number of Subjects: 30	Approximate Duration of Subject Participation: 48 weeks
Approximate Study Centers: 10 in the US	Approximate Duration of Study: 18 months
Design: This is a multicenter, multiple dose, open label study to examine the effects of Acthar in adult subjects with severe NIPPU. Approximately 30 subjects will be enrolled. Subjects with current severe NIPPU who meet entry criteria will be treated with Acthar 1 mL (80 units [U]) subcutaneously (SC) 2x/week for 36 weeks. Followed by a taper to Acthar 1 mL (80 U) SC once a week for 2 weeks, then 0.5 mL (40 U) SC once a week for 2 weeks. All subjects will have a follow-up contact 28 (\pm 14) days after their last dose of study drug.	
Objectives:	
Primary Objective	Endpoints
To explore the efficacy of Acthar in subjects with severe NIPPU in reducing aqueous and vitreous indicators of inflammation.	Proportion of subjects with a 2 or more step reduction from baseline (or achievement of Grade 0) in vitreous haze at 36 weeks. Proportion of subjects with a 2 or more step reduction from baseline (or achievement of Grade 0) in aqueous flare at 36 weeks. Proportion of subjects with a 2 or more step reduction from baseline (or achievement of Grade 0) in aqueous cells at 36 weeks.
Secondary Objective	Secondary Endpoints
To further explore the safety and tolerability of Acthar in subjects with severe NIPPU.	Incidence and severity of ocular adverse events (AEs). Incidence and severity of other AEs. New or worsening cataracts. Mean change in intra-ocular pressure (IOP).
Exploratory Objectives	Exploratory Endpoints
[REDACTED]	[REDACTED]

Study Title: A Multicenter, Open Label Pilot Study to Explore the Efficacy and Safety of Acthar® in Subjects With Severe Noninfectious Intermediate Uveitis, Posterior Uveitis, or Panuveitis	
Protocol MNK61074105	Type: Phase 4
Condition/Disease:	Severe Noninfectious Intermediate Uveitis, Posterior Uveitis, or Panuveitis (NIPPU)
[REDACTED]	[REDACTED]
Entry Criteria:	

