Male or nonpregnant, nonlactating female subjects 18 years of age or older with who have been diagnosed with current severe NIPPU and have active disease at the Baseline Visit as defined by the presence of at least 1 of the following parameters in at least one eye despite at least 2 weeks of maintenance therapy with oral prednisone (or oral corticosteroid equivalent):	
Active, inflammatory, chorioretinal and/or inflammatory retinal vascular lesion.	
≥ 2+ anterior chamber cells (Standardization of Uveitis Nomenclature [SUN] criteria).	
≥ 1.5+ vitreous haze.	
Subjects must be willing to taper their current doses of corticosteroid and immunomodulatory therapy to the minimum effective dose during the study.	
Subjects may be under treatment with any immunosuppressants, immunomodulators, or biologic agents for a comorbid condition as long as they are on a stable dose for 2 weeks prior to screening. Subjects with proliferative or severe nonproliferative diabetic retinopathy, clinically significant macular edema due to diabetic retinopathy, neovascular/wet age-related macular degeneration, abnormality of vitreoretinal interface with the potential for macular structural damage independent of the inflammatory process or severe vitreous haze that precludes visualization of the fundus at the Baseline Visit will be excluded.	
Subjects with Type 1 or Type 2 diabetes mellitus, tuberculosis, history of hepatitis, peptic ulcer, active infection, or any contraindication for Acthar will be excluded.	

Study Title: A Multicenter, Open Label Pilot Study to Explore the Efficacy and Safety of Acthar® in Subjects With Severe Noninfectious Intermediate Uveitis, Posterior Uveitis, or Panuveitis	
Protocol MNK61074105	Type: Phase 4
Condition/Disease:	Severe Noninfectious Intermediate Uveitis, Posterior Uveitis, or Panuveitis (NIPPU)

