Statistical Methods: Analysis Populations The Modified Intent-to-Treat (mITT) Population will include all subjects who receive at least 1 dose of study drug and who contribute any postbaseline efficacy data to the study. The Per-Protocol Population will include the subset of the mITT population who complete the study as per protocol, have no missing primary endpoint data, and do not have any major protocol deviations. The Safety Population will include all subjects who receive 1 or more doses of study drug.	

Study Title: A Multicenter, Open Label Pilot Study to Explore the Efficacy and Safety of Acthar® in Subjects With Severe Noninfectious Intermediate Uveitis, Posterior Uveitis, or Panuveitis	
Protocol MNK61074105	Type: Phase 4
Condition/Disease:	Severe Noninfectious Intermediate Uveitis, Posterior Uveitis, or Panuveitis (NIPPU)
Sample Size A total of 30 subjects will be enrolled in this study. No formal sample size calculations were performed. The sample size was determined empirically.	
Efficacy Analysis	
All efficacy analyses will be performed on the mITT population. Selected analyses will be performed on the Per-Protocol population.	
The primary efficacy endpoints will include:	
Proportion of subjects with a 2 or more step reduction from baseline (or achievement of Grade 0) in vitreous haze at 36 weeks.	
Proportion of subjects with a 2 or more step reduction from baseline (or achievement of Grade 0) in aqueous flare at 36 weeks.	
Proportion of subjects with a 2 or more step reduction from baseline (or achievement of Grade 0) in aqueous cells at 36 weeks.	
The primary efficacy endpoints will be analyzed on both mITT population and the Per-Protocol population. The endpoints will be summarized with frequency tables and evaluated with one-sample binomial test. The nominal p-values along with the 95% confidence intervals (CI) will be provided.	
For subjects with both eyes affected, the change from baseline will be determined based on the eye with the worst severity at baseline. If both eyes have the same severity at baseline, the right eye will be used to determine change from baseline. The same principle will be applied to efficacy endpoints when change from baseline is evaluated.	
Other efficacy endpoints will be summarized with descriptive statistics and the changes from baseline will be evaluated with test statistics and/or 95% CI as appropriate.	
Safety Analysis	

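### Does judging response on the eye that was worse at baseline, with no visible fellow-eye analysis, undermine the primary response rates?

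*Combined protocol and SAP*

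**What the plan says.** The Synopsis defines each primary endpoint as a proportion of subjects, for example "Proportion of subjects with a 2 or more step reduction from baseline (or achievement of Grade 0) in vitreous haze at 36 weeks", with parallel wording for aqueous flare and aqueous cells.

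The eye rule stands under Efficacy Analysis: "For subjects with both eyes affected, the change from baseline will be determined based on the eye with the worst severity at baseline". Ties are settled by "If both eyes have the same severity at baseline, the right eye will be used to determine change from baseline", and the rule is extended by "The same principle will be applied to efficacy endpoints when change from baseline is evaluated".

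Entry requires "presence of at least 1 of the following parameters in at least one eye", so both unilateral and bilateral disease can enrol. Background treatment is to be reduced during the study: "Subjects must be willing to taper their current doses of corticosteroid and immunomodulatory therapy to the minimum effective dose during the study".

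The primary endpoints are analysed in the mITT and Per-Protocol populations with a one-sample binomial test, nominal p-values and 95% confidence intervals. The 30 subjects were chosen without a formal calculation. The exploratory objectives and endpoints are redacted.

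**The concern.** The treatment is given subcutaneously and so reaches both eyes, while background corticosteroid and immunomodulatory therapy is tapered. A fellow-eye flare would then bear on whether the subject has done well. Under the rule, an index eye going from 3+ to 1+ makes the subject a responder even if the other eye goes from 1+ to 3+. The Per-Protocol repeat does not reveal this, because it changes the population and keeps the eye.

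Two details add to the impression of a gap. The rule speaks only of subjects with both eyes affected, so a new flare in the healthy eye of a unilateral subject has no stated place. It also does not name the parameter that defines the worst eye. If a single overall index eye were used, the cells or flare endpoint could be judged on the eye that is milder for that parameter.

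If many responders had a deteriorating fellow eye, the reported rate would describe index eyes and overstate the benefit to subjects.

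**Working it through.** **1. Is anything in the rule wrong?** The plan states no response rate, null proportion or power, so there is no figure of its own to reproduce. The rule itself can be checked against what it must do:

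- One eye per subject gives 30 independent observations, which the one-sample binomial test and its interval need.
- The eye is fixed by baseline severity and then by side. Nothing observed after baseline can influence the choice.
- With one affected eye, the eye to analyse is evident.
- The sentence extending the principle to efficacy endpoints reads most naturally as endpoint by endpoint: worst eye for haze when haze is analysed, worst eye for cells when cells are analysed.

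**2. How much could the rule hide?** Compare it with a stricter definition in which fellow-eye worsening of 2 or more steps at week 36 counts as non-response.

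Inputs: N = 30 from the Synopsis. Everything else is assumed: index-eye response 50%, all subjects bilateral, a proportion pW of fellow eyes worse, and change in the two eyes bivariate normal with correlation ρ.

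P(index responds and fellow worsens) = pW − Φ₂(0, z(pW); ρ), where Φ₂ is the bivariate normal distribution function and 0 is the cut-off for 50% response.

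| pW | ρ | Probability = fall in rate | × 30 subjects | ÷ 0.5 = share of responders |
|---|---|---|---|---|
| 10% | 0.3 | 0.0292 | 0.88 | 5.84% |
| 10% | 0.5 | 0.0162 | 0.49 | 3.24% |
| 10% | 0.7 | 0.0053 | 0.16 | 1.06% |
| 10% | 0.9 | 0.0001 | 0.003 | 0.02% |
| 20% | 0.3 | 0.0664 | 1.99 | 13.3% |
| 20% | 0.5 | 0.0436 | 1.31 | 8.7% |
| 20% | 0.7 | 0.0208 | 0.62 | 4.2% |
| 20% | 0.9 | 0.0019 | 0.06 | 0.4% |

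If half the subjects are bilateral, the fall at pW = 10% halves to 1.46, 0.81, 0.27 and about 0 percentage points.

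**3. The extreme.** A fall of 10 points (0.5 × 1.0 × 0.20 = 0.10, or 3 of 30) needs all subjects bilateral and 20% of responders with a worsened fellow eye. With pW = 20% this is the case ρ = 0, where the two eyes change independently.

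A cruder count sets the share directly, with no correlation model: responders × share bilateral × share with a worsened fellow eye. For 15 responders:

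- low: 15 × 0.5 × 0.05 = 0.375, rate (15 − 0.375)/30 = 48.75%
- high: 15 × 0.9 × 0.20 = 2.7, rate (15 − 2.7)/30 = 41.0%

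For 12 to 18 responders the range is 12 × 0.5 × 0.05 = 0.3 to 18 × 0.9 × 0.20 = 3.24 subjects, or 1 to 10.8 points.

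**4. Against sampling error.** The Clopper-Pearson 95% interval is 31.3% to 68.7% for 15/30, a width of 68.7 − 31.3 = 37.4 points. For 14/30 it is 28.3% to 65.7%. Even the extreme fall stays inside the interval for 15/30.

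**5. Can the absence be established?** No. The synopsis is the only part available, and its exploratory endpoints, where a per-eye or fellow-eye summary could sit, are blacked out. Redacted or unavailable text cannot be counted as missing from the plan.

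**The case for a change.** The strongest argument for the concern is that sampling error does not answer it. A wide interval does not tell the reader how many counted responders had a worsened fellow eye, whereas a simple count would. Nor do the safety analyses supply that count. Ocular adverse events are a secondary endpoint and ophthalmology examinations are safety assessments, so fellow-eye flares may well be recorded, but no visible text links them to responder status. The direction is also fixed: against a definition that forbids fellow-eye worsening, the one-eye rule can only raise the rate or leave it unchanged.

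The first part stands as a reporting preference. A descriptive count by endpoint would be informative and cheap, and a sentence stating that the index eye is chosen per parameter would remove any doubt. Neither point shows an error. The argument from direction proves little, because any responder definition gives a rate at least as high as the same definition with a further failure condition added. Against an eye-level analysis, the direction is unknown. Systemic treatment also cuts both ways: if shared exposure makes the two eyes move together, the table above shows the discrepancy shrinking towards zero.

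**Conclusion.** The concern does not hold. The worst-eye rule with a right-eye tie-break is pre-specified, deterministic and suited to a subject-level binomial analysis. Followed as written, it gives a sound response rate for the eye that was worse at baseline, in an open-label pilot of 30 subjects with nominal p-values. What remains is a wish for supplementary tables, whose absence the available text cannot show, and for slightly more explicit wording on index-eye selection, which the plan already implies.

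On assumed inputs (50% response, all bilateral, 10% of fellow eyes worse), fewer than one subject in 30 would change status at any correlation from 0.3 to 0.9. At 20% worsening it is at most about two. The 10-point extreme requires the two eyes to change independently. New flares in subjects with unilateral disease are not modelled, and no rate of fellow-eye worsening is given in the documents, so these figures indicate scale only.
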